
Our prior work has shown that adherence to fecal testing declines rapidly with successive rounds of screening,¹² which highlights the potential of a blood-based test with high-compliance for capturing non-adherent individuals. The performance of the Septin9 blood test was first studied in 7941 asymptomatic individuals, which found an age-standardized 48% sensitivity and 92% specificity for CRC.¹³ These results were based on an assay that defined test positivity as one of two samples with a positive result. A subsequent study has shown that redefining test positivity as one of three samples with a positive result yielded 68% sensitivity and 79% specificity for CRC.¹⁴ The current FDA-approved Epi proColon assay uses three samples. In a trial that compared the blood test to FIT in individuals who were either recently diagnosed with

PROTOCOL TITLE: Assessing the effect of offering a blood-based colorectal cancer screening test

CRC or were undergoing screening colonoscopy, the blood test was found to be non-inferior to FIT with respect to sensitivity (73% vs. 68%) for CRC but had lower specificity (82% vs. 97%).¹⁵ Two studies have evaluated uptake of the blood test compared to FIT. In a German study of 109 individuals who refused screening colonoscopy, 83% chose the blood test and 15% chose FIT. In a multi-center randomized controlled trial conducted in the US, patients who were overdue for screening were assigned to either the blood test or FIT. Test completion rate was 99.5% for the blood test and 88% for FIT. Of the 30 individuals who had a positive blood test, 20 (67%) scheduled or completed a diagnostic colonoscopy within 3 months.

4) Inclusion and Exclusion Criteria

Inclusion criteria (based on review of the electronic health record):

- Age 50-75
- Declined CRC screening (both colonoscopy and FIT) in the previous 6 months, which must be documented in the electronic health record

Exclusion criteria (based on review of the electronic health record data and self-reported questionnaire data):

- Personal history of colonic adenomas (including sessile serrated adenomas), proximal hyperplastic polyps, CRC, inflammatory bowel disease, or hereditary gastrointestinal cancer syndrome
- First degree relative with CRC diagnosed at <60 years of age; family history of hereditary gastrointestinal cancer syndromes.

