The proposed study is a randomized controlled trial that will 1) assess the uptake of a CRC screening blood test among patients who have declined both colonoscopy and FIT in the previous 6 months, including diagnostic evaluation of positive results and 2) survey patients about their beliefs and attitudes regarding CRC screening and testing options. All participants will be primary care patients at the VA NY Harbor Health Care System. Based on a recent internal audit, there were 1502 patients who had at least one primary care visit from August 2016 through August 2017 and were not up to date with CRC screening. Up to date CRC screening is defined as either 1) a colonoscopy within the past 10 years or 2) FIT within the past year. We will perform an updated CRC screening audit at the beginning of the study to obtain the entire pool of eligible patients who are not up to date with screening. Eligible patients will then be randomized 1:1 to either an intervention group or a control group. All patients will receive a letter noting that they are not up to date on screening and encouraging them to contact a study number if they choose to screen with colonoscopy or FIT. Patients who call will speak to a research assistant who is trained in patient navigation and can facilitate referrals for colonoscopy or FIT. Following the sequential testing approach, letters addressed to the intervention group will also include an option to participate in the blood test, with instructions to call the study number to schedule the blood draw. In addition to the letter, both groups will also receive a follow-up telephone call that reiterates information in the letter. The research assistant will make and receive all calls using a standard script. All patients will also be asked to complete a questionnaire about their beliefs and attitudes regarding CRC screening (see Appendix). The questionnaire will be mailed with the invitation letter and will also be administered over the telephone by the research assistant. The study team will notify patients and their primary care physicians of blood test results and will facilitate a colonoscopy referral for those with positive tests. Primary care physicians will not be asked to notify the patients or make the colonoscopy referral because most will not have adequate knowledge of the Septin9 test to provide appropriate patient education.

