Patients will be informed of the potential risks as part of the informed consent process. All efforts will be made to ensure patient confidentiality and assurance of HIPAA compliance. Participant data will be de-identified using a protocol-specific unique code that will be used for all further data management. A list matching the patient medical record number to the protocol specific unique code will be maintained in a password-protected file in the PI's private drive on the VA network. There will be no data entry or interpretation outside of the VA NY Harbor Health Care System. The names of the patients will not be revealed in written reports or publications detailing the research findings.

21) Provisions to Protect the Privacy Interests of Subjects

The study team will take every possible precaution to protect the privacy of study participants. Only study team members who have been trained by the PI will be allowed to access patient data. Participants data will be de-identified for analysis and only aggregate data will be presented for publication. In addition, participants will not be required to answer any questionnaire question that may make him/her not at ease.

22) Compensation for Research-Related Injury

N/A

23) Consent Process

We are requesting waiver of HIPAA and informed consent for the purpose of screening patients who are eligible for participating in the study. For the control arm, we are requesting waiver of HIPAA and informed consent to access their medical record and determine whether they undergo a colonoscopy for FIT within 6 months of the initial invitation letter. For participants in the intervention arm who elect to undergo the blood test, written informed consent and HIPAA authorization will be obtained onsite prior to phlebotomy. All patients will also be invited to participate in a short anonymous questionnaire by mail and if needed, by phone. A one-page description of the questionnaire and how to contact the research team will be provided in the mailing and reiterated in the phone call. However, we are requesting waiver of documentation of consent for the anonymous questionnaire.

24) Drugs or Devices

N/A

PROTOCOL TITLE: Assessing the effect of offering a blood-based colorectal cancer screening test

REFERENCES

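### Section 23 calls the questionnaire anonymous, but section 4 uses it as a source of exclusions and section 9 mails it after randomization; reconcile before mailing

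*Combined protocol and SAP*

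**What the plan says.** Section 23 (Consent Process) describes the form in these words: "All patients will also be invited to participate in a short anonymous questionnaire by mail and if needed, by phone". It uses the same adjective in its request to the review board: "However, we are requesting waiver of documentation of consent for the anonymous questionnaire".

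Section 4 (Inclusion and Exclusion Criteria) heads the exclusion list with "Exclusion criteria (based on review of the electronic health record data and self-reported questionnaire data".

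Section 9 (Procedures Involved) gives the order of events. First, "Eligible patients will then be randomized 1:1 to either an intervention group or a control group". Then the letters go out, and "The questionnaire will be mailed with the invitation letter and will also be administered over the telephone by the research assistant".

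Section 20 (Confidentiality) sets up a code for study data in general: "Participant data will be de-identified using a protocol-specific unique code that will be used for all further data management". A list matches the code to the medical record number. Neither section 20 nor section 23 says that the questionnaire carries this code.

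For Aim 2, section 8 makes demographic and health-related predictors of accepting the blood test in the intervention group the primary outcome. The Data Analysis text in section 11 plans a multivariable logistic regression for it. The Sample Size Calculations select variables by their association with completion of the blood test. No list of covariates is given.

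**The concern.** A patient can be excluded on a questionnaire answer only if the study team knows whose answer it is. Section 4 assumes that they do, and section 23 tells patients and the review board that they do not.

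The order of events adds a second difficulty. The form reaches patients only after allocation, so an exclusion based on it would be an exclusion of a randomized patient. It could touch only those who returned a form or answered by telephone. The two arms receive different letters, since only the intervention letter offers the blood test, so return could differ by arm. Removing patients on that basis would weaken the randomized comparison of screening rates, which is the primary outcome of Aim 1.

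For Aim 2, the outcome (a completed blood draw) is held in study records. A predictor that exists only on the form must be joined to that record patient by patient. An uncoded mailed form cannot be joined later, so the decision has to be made before mailing.

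**Working it through.** The main point is one of consistency, so the texts are set side by side first.

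**Exclusions**

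1. *Form anonymous, as section 23 says.* No answer can be traced to a patient, so the questionnaire part of section 4 cannot be carried out. No one is removed on a form, and Aim 1 is unaffected.
2. *Form linkable, for example through the section 20 code.* Section 4 can be carried out, but only after randomization and only for responders. Section 23, the waiver request and the one-page description then misdescribe the form, because a coded form is not anonymous.

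Under either reading, at least one section must change.

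**Possible size in Aim 1 (second case only).** The documents give no return rate and no expected number of questionnaire-based exclusions. As an illustration, assume 10 removals in one arm, which equals the drop-out allowance (180 − 170 = 10), and use the plan's 50% uptake as that arm's screening rate.

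- All randomized: 0.50 × 180 = 90 screened; 90/180 = 50.0%.
- Ten unscreened patients removed: 90/170 = 52.9%.
- Ten screened patients removed: 80/170 = 47.1%.

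The extreme shift is 2.9 percentage points in either direction, against the 15-point difference the trial is powered to detect. Removals unrelated to screening would shift nothing on average.

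**Aim 2: does the form record the outcome?** In the appendix, items 19, 20 and 22 ask what the patient would do. Section 8 lists willingness as a separate secondary outcome. Two questions in the section 8 table are instead worded as decisions already made, but the visible appendix items are not. Completion therefore has to come from study records.

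**Aim 2: the plan's figures.** The 170 per group reproduces for 50% against 35%, two-sided 5%, 80% power, without continuity correction:

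n = [1.96 × √(2 × 0.425 × 0.575) + 0.8416 × √(0.50 × 0.50 + 0.35 × 0.65)]² / 0.15² ≈ 169.3, rounded up to 170.

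Expected takers are 0.50 × 170 = 85. Non-takers are also 85, so 85 is the number of events for the plan's rule. 85/10 = 8.5, hence at most 8 variables. This holds for predictors taken from the record.

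If form predictors are used and forms are coded, only returned forms count. With assumed return rates, and return unrelated to uptake:

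| Return | Events (85 × rate) | Variables at 10 per variable |
|---|---|---|
| 100% | 85 | 8 |
| 80% | 68 | 6 |
| 60% | 51 | 5 |
| 40% | 34 | 3 |
| 20% | 17 | 1 |

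**The case against.** The strongest reply is that *anonymous* is one loose word. Section 20 applies a code to participant data, and the research assistant telephones known patients, so the form may have been meant as coded all along. That is plausible, but it does not settle the matter: section 23 would then misdescribe the form, and the exclusions would still come after randomization.

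A second reply is that the plan nowhere says randomized patients will be removed. It says eligible patients are randomized, which suggests that eligibility is settled beforehand. This is fair. A reader might infer that the Aim 1 analysis will be biased; the documents show only that section 4, followed literally with a linkable form, would permit it. Nor do the two harms add up, since each needs the opposite premise about the form.

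A third reply concerns Aim 2, and most of it stands. A reader might infer that the Aim 2 primary model fails. The documents do not support that. Self-rated health and self-perceived cancer risk are named only as stratifiers of secondary outcomes, which works on an anonymous form because stratifier and answer are on the same sheet. Age, race, ethnicity and visit counts could plausibly come from the record. Telephone interviews have no stated timing and could follow the patient's decision, so some acceptance might be captured on the form. The Aim 2 point is therefore conditional.

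Finally, the copy reviewed shows the appendix form only from item 14 on. An identifier field or eligibility questions may appear earlier. An identifier would remove the linkage problem but would also contradict *anonymous*.

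**Conclusion.** The inconsistency stands and should be fixed before the forms are mailed. Sections 4, 9 and 23 cannot all be followed: the questionnaire-based exclusions are either impossible or applied after randomization to responders only.

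The effect on Aim 1 arises only if the form is linkable and is used to remove patients. Its size cannot be derived from the documents; the 2.9-point figure is an extreme for an assumed 10 removals in one arm, not an estimate.

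For Aim 2, the loss is limited to predictors that exist only on the form, if any are intended. A record-based model of up to 8 variables at the planned uptake remains possible. With a coded form, the limit falls with the return rate, which the plan does not state.

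The basis for record access in intervention patients who decline the blood test is a separate question and is not part of this point.

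**What to change.** 1. In section 4, base trial eligibility on record data available before randomization and delete the questionnaire as an exclusion source for the trial. State that all randomized patients stay in the Aim 1 comparison whatever a returned form says. How an answer bears on a patient's care is for the investigators and is separate from the analysis set.
2. Before mailing, choose one of two routes. Either print the section 20 code on each form and replace *anonymous* with *confidential, coded* in section 23, the waiver request and the one-page description, subject to review-board agreement. Or keep the form anonymous and limit the Aim 2 model to record-derived predictors.
3. Define the Aim 2 model outcome as a completed blood draw from study records, and state the source of each candidate predictor. If form predictors are used, count events for the 10-per-variable rule only among intervention patients with linked forms.

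The cost is a printed code, short wording changes and review-board re-review. Some patients may be less willing to answer a coded form. Exclusion facts that are missing from the record would no longer be caught through the form for trial purposes. No stated sample size changes.

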14) Have you ever had a stool-based test (e.g. fecal occult blood test/FOBT or fecal immunochemical test/FIT)?

Yes No (SKIP to 15)

14a) How long ago was your last stool-based test?

Less than 12 months More than 12 months

15) Why did you decide not to do a colonoscopy when offered in the past 6 months?

I don't want to take the bowel prep
I don't want to know if I have colorectal cancer
Colonoscopy is painful
I don't have time
I don't have an escort
I'm at low risk and don't need screening
Other
I wasn't offered the test in the past 6 months

16) What would make you change your mind and get a colonoscopy?

If the bowel prep were easier
If I knew colonoscopy can prevent cancer by removing pre-cancerous polyps
Overcoming my fears about colonoscopy
If my doctor recommended it
If I knew it wasn't going to hurt
If I had time/could get time off from work
If I could find an escort
Other
Nothing would change my mind

17) Why did you decide not to do a stool test (fecal immunochemical test/FIT) when offered in the past 6 months?

I don't want to handle stool
I don't want to know if I have colorectal cancer
The directions for the stool test was too complicated
I don't think a stool test is accurate
I don't have access to a toilet that's suitable for collecting the stool sample
Other
I wasn't offered the test in the past 6 months

18) What would make you change your mind and take a stool test?

If the directions for the stool test was easier to understand
If I knew the stool test was accurate
If I had access to a toilet that's suitable for collecting the stool sample
Other
Nothing would change my mind

PROTOCOL TITLE: Assessing the effect of offering a blood-based colorectal cancer screening test

19) Would you take a blood test to screen for colorectal cancer?

Yes No (SKIP to 22)

20) Why would you take the blood test?

A blood test is easy/convenient
 A blood test is not painful
 A blood test is accurate
 Other

21) What do you think are the advantages of a blood test compared to colonoscopy and stool test?

It's more convenient than a colonoscopy or a stool test
 I don't have to do any special preparation to take the test
 I'm used to getting blood tests
 I think blood tests are more accurate than other tests
 The test is done by a medical professional and I don't have to do anything myself
 Other

22) Why would you not take a blood test?

I don't like getting my blood drawn
 I don't think a blood test is as accurate as a colonoscopy or stool test
 I don't want to know if I have colorectal cancer
 Other

23) What would make you change your mind and take a blood test?

If I knew the blood test is better than colonoscopy and the stool test
 If my primary care physician recommended the test
 Other
 Nothing would change my mind

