Primary outcome: Screening rate in the intervention group vs. control group after 6 months.

Secondary outcomes:

A) Complete screening rate in both groups, which is defined as completion of the entire screening strategy. For colonoscopy, this requires cecal intubation and an adequate bowel preparation. For individuals who took Septin9 and FIT, positive results must be followed by a colonoscopy with cecal intubation and adequate bowel preparation.

B) Among individuals in the intervention group who had a positive blood test, proportion who completed a follow-up colonoscopy within 6 months.

C) Endoscopic and pathologic findings among individuals in the intervention group who had a diagnostic colonoscopy.

Aim #2: *To survey screen-resistant patients to understand their beliefs and attitudes about CRC screening and testing options.* Both intervention and controls groups will be invited to complete a brief questionnaire. Questionnaire questions are shown in the Table and are adapted from a previous study that offered both the blood test and FIT to patients who had refused screening colonoscopy.⁴ All response options will be presented in a multiple-choice format. The full questionnaire is shown in the Appendix.

Primary outcome: Demographic and health-related predictors of accepting the blood test in the intervention group.

Secondary outcomes:

A) Proportion of both groups who answered that they would be willing to take a blood test for colorectal cancer screening

B) The most commonly cited advantages of a blood test compared to colonoscopy and stool test in both groups

C) The most commonly cited reasons for not taking the blood test in the intervention group. In an exploratory analysis, we will stratify results by race/ethnicity, self-reported health, frequency of healthcare access, and self-perceived risk of CRC.

Table. Select Questionnaire Questions

Demographics
What is your age?
What is your race?
What is your ethnicity?
Health status and medical history
How would you rate your overall health?
How many visits have you had with your primary care doctor in the past year?
What do you think is your own risk of getting colorectal cancer?
Colorectal cancer testing
Have you ever had a colonoscopy? If so, when?
Have you ever had a stool-based test? If so, when?

PROTOCOL TITLE: Assessing the effect of offering a blood-based colorectal cancer screening test

Why did you decide not to do a colonoscopy when offered in the past 6 months?

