What would make you change your mind and get a colonoscopy?
Why did you decide not to do a stool test (fecal immunochemical test/FIT) when offered in the past 6 months?
What would make you change your mind and take a stool test?
Why did you decide to take a blood test?
What are the advantages of a blood test compared to colonoscopy and stool test?
Why did you decide not to take a blood test?
What would make you change your mind and take a blood test?

9) Procedures Involved

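### A 'No' at questionnaire item 19 skips the item on advantages, so Aim 2 secondary outcome B would describe only patients who already say they would take the blood test

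*Combined protocol and SAP*

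**What the plan says.** Section 8 (Study Endpoints) gives Aim 2 as a survey of the beliefs and attitudes of screen-resistant patients, with both randomised groups invited to answer. Secondary outcome B is "The most commonly cited advantages of a blood test compared to colonoscopy and stool test in both groups". Secondary outcome C is "The most commonly cited reasons for not taking the blood test in the intervention group". The table of selected questions in Section 8 words the item behind outcome C as "Why did you decide not to take a blood test".

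The Appendix questionnaire carries the corresponding items:

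- Item 19: "19) Would you take a blood test to screen for colorectal cancer", with the answers and routing printed as "Yes No (SKIP to 22" (closing bracket follows).
- Item 20 asks for reasons for taking the test.
- Item 21: "21) What do you think are the advantages of a blood test compared to colonoscopy and stool test". Its options are five possible advantages and 'Other'.
- Item 22: "22) Why would you not take a blood test".
- Item 23: "23) What would make you change your mind and take a blood test".

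No stop or skip is printed after item 21. Under Data Analysis in Section 11, the Aim 2 secondary outcomes are to be summarised descriptively, with stratification by patient characteristics. No rule says whose answers to items 21 to 23 count. Section 9 has the form mailed with the invitation letter and also administered by telephone. Section 23 describes it as anonymous.

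**The concern.** Outcome B names both groups without limiting them to willing patients, but the form lets only willing patients answer the item that feeds it. Aim 2 exists to learn what people who have refused colonoscopy and FIT think about the alternatives. Those who would refuse the blood test as well are the most informative part of that population, and the printed skip removes them from this outcome. A reader given the ranking of advantages as a result for both groups would not know that it came only from people inclined towards the test.

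The loss happens at data collection. Tabulating by item 19 can separate answers that were given, but it cannot create item 21 answers for people who were never asked.

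Outcome C has a lesser problem of wording. It concerns reasons for a decision that has been made, as does the question in the Section 8 table, while item 22 asks about a hypothetical refusal.

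**Working it through.** **Routing as printed.** Following each answer at item 19 through the form:

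| Answer at item 19 | Item 20 | Item 21 | Item 22 | Item 23 |
|---|---|---|---|---|
| Yes | asked | asked | asked | asked |
| No | skipped | skipped | asked | asked |

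**Set against the Aim 2 secondary outcomes.**

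- Outcome A (willingness) uses item 19, which comes before the skip and goes to everyone. It is unaffected.
- Outcome B uses item 21. It is reached by willing respondents in both arms and by no unwilling respondent in either.
- Outcome C uses item 22 in the intervention arm. It is reached by all respondents, willing or not.

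**Size of the gap in outcome B.** Let *w* be the proportion of respondents answering 'Yes' at item 19 and *r* the questionnaire response rate. With 180 patients per arm (Section 5), the number per arm not asked item 21 is 180 × *r* × (1 − *w*), and the share of respondents missing is 1 − *w*. The plan states neither *w* nor *r*, so the values below are assumptions. The middle row borrows the 50% uptake from Sample Size Calculations in Section 11, which is expected uptake and not stated willingness.

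| *w* | Share missing | Asked / not asked per arm, *r* = 100% | Asked / not asked per arm, *r* = 50% |
|---|---|---|---|
| 30% | 70% | 54 / 126 | 27 / 63 |
| 50% | 50% | 90 / 90 | 45 / 45 |
| 70% | 30% | 126 / 54 | 63 / 27 |

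For example, at *w* = 30% and *r* = 100%: 180 × 1 × 0.70 = 126.

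**Link to the sample size.** The plan's 170 per group is reproduced with 50% against 35% (or 65%), two-sided alpha 0.05, 80% power, pooled variance and no continuity correction. For 50% against 35%, the formula is [1.960 × √(2 × 0.425 × 0.575) + 0.842 × √(0.50 × 0.50 + 0.35 × 0.65)]² ÷ 0.15² = 169.3, rounded up to 170. No questionnaire item enters that calculation.

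**Outcome C.** Two kinds of patient show why item 22 is only a proxy. One answers 'Yes' at item 19 but never has the blood draw, and belongs in outcome C. The other answers 'No' and later accepts, and does not belong there. Because the form goes out with the invitation, it may be filled in before any decision. Because it is called anonymous and no link to uptake is described, the answers cannot clearly be sorted afterwards by what the patient did.

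**The case against.** The strongest reply on outcome B is that the two groups it names are the randomised arms, and item 21 reaches both through their willing members. Asking about advantages only of people who would take a test is a common survey choice. Outcome B ranks advantages and does not measure how well the test is liked; outcome A does that, from an item put to everyone. Item 21 also has no option for seeing no advantage, so giving it unchanged to someone who has just said 'No' would force a choice, an 'Other' or a blank. Much of this stands. No arm is missed, the routing does not by itself inflate a measure of favour, and the item needs an extra option before it is widened. But the outcome as written is not limited to the willing, and the views of the unwilling on this question are lost.

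A reader might go further and infer that the missing skip after item 21 leaves outcome C unmeasured in the group it names, or hopelessly mixed. The documents do not support that. Unwilling intervention patients do answer item 22, and willing patients' answers can be set apart using item 19. The open routing is even useful, because it keeps patients who say 'Yes' and never test. Nor can it be said that half of the item 22 answers would come from people to whom it does not apply: that assumes willing patients answer it as often as unwilling ones, and Section 21 lets participants leave out questions they are uneasy with.

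The part of the questionnaire before item 14 and the telephone script were not available here, so an instruction for 'Yes' respondents may exist there. The printed skip for 'No' stands either way.

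**Conclusion.** The point holds for outcome B: as printed, it is collected from a selected subset of each arm, and the selection cannot be undone at analysis. The share of respondents missing equals one minus willingness, or 30% to 70% over an assumed willingness of 70% down to 30%. This assumes that the form is used as printed and that the telephone script follows the same skip.

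For outcome C, the point is limited to labelling: the data will be hypothetical reasons, to be shown separately by stated willingness, and should not be presented as reasons for an actual refusal.

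The priority is low. These are descriptive secondary outcomes, and neither the primary comparison of screening rates nor the sample size is touched.

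**What to change.** - **Outcome B.** Ask item 21 of every respondent before the item 19 branch takes effect, and add an option such as 'I see no advantages'. Keeping item 19 first and moving only the skip to after item 21 would avoid listing advantages just before the willingness question.
- **If forms are already in use.** Leave the form alone and report outcome B as 'among those willing to take a blood test', with that denominator, beside outcome A.
- **Outcome C.** Tabulate item 22 in the intervention arm by item 19 answer, state the denominators, and describe the results as hypothetical reasons. Do not send all 'Yes' respondents past item 22, which would lose those who agree in principle but do not test. Simply substituting the past-tense question from the Section 8 table would not work on a form mailed with the invitation and described as anonymous.

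The cost is one more item for unwilling respondents and IRB notification of the revised form. The labelling changes cost only a few lines in the analysis plan.
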